Next-generation sequencing (NGS) has brought genetic testing to new frontiers, expanding the scope of detectable genomic variants. Moreover, its significant reduction in costs over the years has facilitated the implementation of genetic diagnostic testing. Our customized shallow read-depth genome sequencing analytical pipeline, namely low-pass genome sequencing (GS), enables efficient and cost-effective detection of genome-wide copy-number variants (CNVs, >50 kb) and low-level chromosomal mosaicisms (as low as 10%). Furthermore, the roles of cryptic structural rearrangements, absence of heterozygosity (AOH), and single-nucleotide variant (SNV) were less understood in current studies.

Various versions of sequencing platforms targeting at different variants were already established and validated in the Prenatal Genetic Diagnostic Laboratory, The Chinese University of Hong Kong, including FetalSeq, ChromoSeq, and 30xWGS.

Human endometrial and decidual tissues, containing a myriad of immune and inflammatory populations [3-4], are immunologically dynamic. In the early proliferative phase of the menstrual cycle, T-cells are the most abundant leukocyte population in the endometrium, but they decrease to 20% of all stromal leukocytes during early pregnancy [5]. Macrophages are also present in endometrial tissues during all phases of the menstrual cycle, but are most abundant in late secretory endometrium and in decidual

tissues during early pregnancy [6]. The most abundant population (70%) of stromal leukocytes observed in late secretory endometrium and in the decidua during early normal pregnancy are large granular lymphocytes (LGL) bearing the unique phenotype: CD56⁺⁺, CD16⁻, CD57⁻, CD2[±], CD38[±], CD3⁻, CD4⁻, CD8⁻ [7-10]. Increased mean numbers of CD56⁺ cells have been reported in secretory endometrium of women with recurrent miscarriages [11].

The hypothesis that the balance between T-cell subsets (i.e. CD4⁺ and CD8⁺ cells) plays a role in maintaining successful pregnancy is controversial. Some studies have reported no difference between the proportions of T-cell subsets in either secretory endometrium or first trimester decidua from women with a history of recurrent pregnancy loss compared with normal controls; while others have described a shift towards a higher ratio of CD8⁺ T-cells in endometrial biopsies from women with a history of recurrent pregnancy loss [12-15].

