The activation status of T-cell populations may provide another indicator of cellular immunity potentially involved in pregnancy loss. The IL-2 receptor has been reported to be absent on T-cells in normal first trimester decidual tissues using immunohistochemical techniques [16]; however, using flow cytometry, CD3⁺CD25⁺ activated T-cells have been identified in decidual tissue [17]. CD69 is another early activation marker expressed on the surface of T-cells [18]. A proportion of T-cells constitutively expresses this marker throughout the menstrual cycle and in normal early pregnancy.

Approximately 60% of spontaneous abortions are attributable to numerically abnormal chromosomes in the developing conceptus [19], yet limited data to date addressing immunological phenomena in the decidua of miscarried women has compared their data relative to well-defined chromosomal abnormalities belonging to conceptuses. This is important since the chromosome abnormality trisomy 16, which occurs in 26% of all spontaneous abortions, is incompatible with life [20] and would thus be an undisputed cause of spontaneous abortion. Therefore, the purpose of our study was to determine whether decidual leukocyte subpopulations and their associated activation markers were different between women having miscarriage of either a trisomy 16 conceptus (47XY+16 or 47XX+16) compared with a chromosomally normal male conceptus (46XY) and compared with gestationally age-matched decidual tissues. Samples from presumably normal female conceptuses (46XX) were not chosen for study because of the inability to accurately differentiate from possible maternal cell contamination.

For managing with miscarriage or termination of pregnancy (TOP) in first trimester loss, ultrasound-guided manual vacuum aspiration (USG-MVA) is one of the treatment options. USG-MVA for the treatment of early pregnancy loss has been used for many decades. It had been reported that USG-MVA is safer, more cost-effective, and is associated with shorter hospitalization time and cost than surgical evacuation under general anesthesia [21, 22]. USG-MVA is a surgical technique of suction curettage. It is performed by using a hand held vacuum source (a syringe with barrel and plunger) attached to a uterine cannula [23, 24] The USG-MVA device works by aspirating the uterine content via the cannula into the syringe. Furthermore, product of conception derived from USG-MVA can be sent for karyotyping analysis.

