B. Study objectives and hypotheses

I. Objective

- (1) To investigate the immune cells profile in decidua derived from early pregnancy loss and correlate the result to the embryo karyotyping.
- (2) To investigate the genetic abnormality spectrum of early pregnancy loss by comprehensive next-generation-sequencing based approaches.

II. Hypotheses

- (1) Decidua tissue is different between euploidy pregnancy and aneuploidy pregnancy.
- (2) Except for well-known genetic abnormalities, early pregnancy loss can be attributed to various genetic etiologies, including cryptic structural rearrangements, absence of heterozygosity (AOH), and single-nucleotide variant (SNV), which can be detected by sequencing approaches.

C. Subjects:

Women undergoing ultrasound-guided manual vacuum aspiration (USG-MVA) will be recruited at Obstetrics and Gynaecology in The Prince of Wales Hospital

I. Inclusion Criteria

- (1) Women 18 years old or above
- (2) Women with miscarriage or TOP who are suitable candidates for MVA
 - first trimester miscarriage or TOP
 - No fetal heart beat or TOP in those with CRL 25mm
 - incomplete miscarriage or TOP with POG <5cm
 - hemodynamically stable,
 - tolerates well with speculum examination

II. Exclusion Criteria

(1) Women who are not feasible for the MVA procedure

- cervical stenosis
- fibroid uterus >12 weeks in size
- known uterine malformation
- bleeding disorder
- clinically sepsis
- inability to tolerate pelvic examination

(2) History of psychological/ psychiatric problem

(3) Patient refusal

D. Sample Size

There are two groups in this study: (1) women who miscarry or TOP with chromosomally normal fetus; (2) women who miscarry or TOP with chromosomally abnormal fetus.

There is no literature data on the difference in leucocytes profile between groups. In calculating the sample size required, we are making an assumption that the degree to which other leucocytes are affected, is similar to that of CD45+ cell count.

According to our pilot result, the CD45+ cell count was 89.7 ± 18.3 in decidual samples from miscarried women with abnormal karyotyping and 102.3 ± 20.2 in miscarriage women with normal fetal karyotyping, respectively. The sample size required for an alpha value of 0.05 and 80% power would be 50 in each arm. Therefore, a total of 100 subjects will be recruited.

E. MVA procedure

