The Drop-seq and 10x sequencing data will be processed using the standard pipeline (Drop-seq core computational protocol V1.2, <http://mccarrolllab.com/dropseq/>) with minor modifications. For Drop-seq Read1, bases 1 to 12 will be tagged with cell-barcode "XC," and bases 13 to 20 will be tagged with UMI "XM." For 10x Read1, bases

1 to 16 will be tagged with cell barcode XC, and bases 17 to 26 will be tagged with UMI XM. Read2 will be trimmed at the 5' end to remove any adaptor sequence, and the 3' end will be trimmed to remove poly(A) sequences of length six or more and then aligned to human (hg38) genome reference using STAR aligner (STAR_2.5.1a), allowing no more than three mismatches. Gene expression matrix will be then generated using the "MIN_BC_READ_THRESHOLD=2" option to retain UMIs with two or more reads.

J. Statistical Analysis

Quantitative data will be expressed as mean \pm standard deviation (SD)/95% confidence interval (CI) if they follow a normal distribution, median \pm inter-quartile range for skewed distribution. The baseline characteristics of the three groups of patients will be compared using the Mann-Whitney test. Differences between groups will be assessed by Student's t-test, ANOVA and non-parametric test where appropriate. P value of <0.05 will be considered statistically significant. Statistical analysis will be performed using SPSS version 26.0.

K. Consents

All subjects will be given a detailed explanation and their permission will be obtained before they are recruited into the study. A written consent form will be signed by the participants. The participants can withdraw from the research without any repercussions.

L. Ethical considerations

(1) Ethical conduct of the study

Risks of blood sample collection will be minimized. Minor discomfort or worrisome may be implied to the patients if blood sample collection is needed. Supports will be given by research team.

The study will be conducted according to the principles of the Declaration of Helsinki and its most recent updates (7th revision, 2013). Investigator(s) will ensure that the study complies with all local, federal, or country regulatory requirements as applicable.

(2) Confidentiality

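### Groups formed by fetal chromosomes are compared with unadjusted tests only, so differences in gestational age or in the miscarriage/TOP mix could be read as an effect of karyotype

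*Protocol*

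**What the plan says.** Hypothesis 1 in Section B reads "Decidua tissue is different between euploidy pregnancy and aneuploidy pregnancy", and Objective 1 is to correlate the decidual immune-cell profile with embryo karyotype. Section D defines the groups by fetal chromosomal status: "1) women who miscarry or TOP with chromosomally normal fetus; (2) women who miscarry or TOP with chromosomally abnormal fetus". Section C admits women aged 18 or over with first-trimester miscarriage or TOP, and sets no upper age limit.

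Section J gives the between-group analysis as "Differences between groups will be assessed by Student's t-test, ANOVA and non-parametric test where appropriate", at P<0.05. Its only other provision for group differences is "The baseline characteristics of the three groups of patients will be compared using the Mann-Whitney test". It does not say what follows if an imbalance is found. Neither Section C, D nor J mentions matching, stratification or covariates.

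The background, in stating the study's purpose, names a further comparator: the losses are to be "compared with gestationally age-matched decidual tissues". Section D contains no such group.

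**The concern.** Fetal karyotype is observed, not assigned. The two groups may therefore differ in how far the pregnancy had progressed and in whether it ended by miscarriage or by termination. If either feature is related to decidual leucocyte counts, an unadjusted test combines that relation with any relation to chromosomes. A baseline significance test can flag an imbalance but does not remove it from the comparison, and ANOVA as named is not a covariate model.

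The protocol itself treats gestational age as relevant, because it wanted an age-matched comparator. It then carries neither matching nor adjustment into the design or analysis. At stake is the interpretation of Objective 1: a significant result could reflect when or how the pregnancy ended. More recruitment would not help, because a larger sample makes a biased difference more likely to reach significance.

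**Working it through.** **Inputs.** From Section D: CD45+ count 89.7 (SD 18.3) with abnormal karyotype and 102.3 (SD 20.2) with normal karyotype; alpha 0.05, 80% power, 50 per arm. The pilot figures are for miscarriages only. I assume two-sided tests. The protocol gives no slope of CD45+ on gestational age and no expected gap between the groups, so both are assumed below.

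**1. The plan's own figure.** Difference = 102.3 − 89.7 = 12.6. Pooled SD = √((18.3² + 20.2²)/2) = 19.27. Standardised difference = 12.6/19.27 = 0.654. A two-sided t-test then needs 38 per arm for 80% power, and 50 per arm gives about 90%. The stated 50 is thus not reproduced from the stated inputs. That is a matter of size, not bias, and is not pursued here; it does mean there is room for covariates.

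**2. False-positive rate under a pure imbalance.** Bias = (slope per week) × (gap in weeks). I assume a 1-week gap, slopes of 0, 2, 4 and 6 units per week, and no true karyotype effect. SE = 19.27 × √(1/50 + 1/50) = 3.85. The rejection probability comes from the noncentral t with 98 df and noncentrality bias/SE.

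| Bias (units) | Share of 12.6 | Bias/SE | P(p<0.05), 50:50 | P(p<0.05), 60:40 |
|---|---|---|---|---|
| 0 | 0% | 0 | 5.0% | 5.0% |
| 2 | 16% | 0.52 | 8.1% | 8.0% |
| 4 | 32% | 1.04 | 17.7% | 17.2% |
| 6 | 48% | 1.56 | 33.8% | 32.7% |

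The 60:40 column (SE = 19.27 × √(1/60 + 1/40) = 3.93) shows that a moderately unequal split changes little.

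**3. The same question without a slope per week.** Let r be the within-group correlation of gestational age with CD45+, and g the between-group gap in SDs of gestational age. Bias = r × g × 19.27. With r = 0.2 and g = 0.25 the bias is 1.0 and the false-positive rate 5.7%. With r = 0.3 and g = 0.5 they are 2.9 and 11.5%. With r = 0.5 and g = 1.0 they are 9.6 and 70%. Producing the whole pilot difference would need r × g = 0.65, which is larger than any pair in this range.

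**4. Larger sample.** With 100 per group, SE = 19.27 × √(2/100) = 2.73. Biases of 2, 4 and 6 are then significant 11%, 31% and 59% of the time.

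**5. Cost of adjusting for gestational age.** Adjusted SE = 19.27 × √(1 − R²) × √(1/n₁ + 1/n₂) × √(1 + g²n₁n₂/N²). R² is the share of within-group variance explained by gestational age, and g = slope × 1 week/(√R² × 19.27). I assume R² of 0.10 or 0.20.

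- Least favourable case (slope 6, R² = 0.10): g = 6/(0.316 × 19.27) = 0.98. At 50:50 the last factor is √(1 + 0.969/4) = 1.114 and SE = 19.27 × 0.949 × 0.2 × 1.114 = 4.08. Power for 12.6 is about 86%; at 60:40 it is about 85%.
- Most favourable case (slope 2, R² = 0.20): about 95% at 50:50 and 94% at 60:40.
- Unadjusted: about 90% at 50:50 and 89% at 60:40.

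These figures cover gestational age only. The cost of adding miscarriage versus TOP depends on how far the two types overlap between groups, which the protocol does not indicate.

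**The case against.** **Left to an SAP.** Section J is a short generic list with a qualifier, and covariates are often specified in an SAP that is not shown here. An absent covariate list alone would not be a finding. But Section J does name the tests for a comparison it knows to be non-randomised, and following it as written gives an unadjusted answer. That part of the objection does not remove the point.

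**Gestational age may not be a confounder in the strict sense.** Karyotype precedes the timing of loss, so gestational age at loss may lie partly on the path from chromosomes to decidua. Adjusting could then remove some of the difference under study. This stands. The unadjusted shift cannot all be called bias, and the adjusted estimate should not replace the unadjusted one.

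**Stronger readings that the protocol does not support.**
- A reader might infer that the background shows leucocytes changing from week to week in the first trimester. The sentence "T-cells are the most abundant leukocyte population in the endometrium, but they decrease to 20% of all stromal leukocytes during early pregnancy" contrasts the early proliferative phase of the menstrual cycle with early pregnancy. It gives no trend within pregnancy.
- A reader might infer that normal and abnormal losses were to be matched to each other. The age-matched tissue is an additional comparator.
- A reader might treat maternal age as an established confounder. The protocol links it to neither karyotype nor leucocytes.
- A reader might conclude that Objective 1 cannot be answered. It is worded as a correlation, and an unadjusted comparison does answer whether the groups differ. It does not show that chromosomes account for the difference.
- A reader might expect adjustment to raise power. That is assured only if the covariates are balanced; in the least favourable case above, power falls slightly.

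The first-trimester and size limits in Section C narrow the gestational range, which reduces the room for imbalance but does not remove it.

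**Conclusion.** The point holds as a weakness of the planned analysis, and the protocol should be changed. Non-randomised groups that mix miscarriage and TOP are to be compared with unadjusted tests, and a gestational-age comparator named in the background has no counterpart in the design or analysis. What is at risk is attributing a difference to fetal chromosomes, not detecting a difference.

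The size is illustrative. False-positive rates of about 5% to 34% at 50:50 rest on an assumed 1-week gap and assumed slopes of 0 to 6 units per week. If the slope or the gap is zero, gestational age causes no problem. The miscarriage/TOP mix could cause a shift of the same kind, which the protocol gives no means of sizing. Maternal age is a secondary consideration only.

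**What to change.** In Section J, prespecify for each leucocyte measure a linear model on chromosomal group, with the outcome log-transformed if skewed. Adjust for gestational age and for miscarriage versus TOP, with maternal age as a secondary covariate. Give one definition of gestational age and use it for every woman, since age at loss and age at procedure can diverge in a missed miscarriage.

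Report the adjusted difference with its 95% CI beside the unadjusted difference. State that gestational age at loss may be partly a consequence of karyotype, and that a group difference will be called independent of gestational age only if it persists after adjustment. If miscarriage and TOP overlap too little between the groups for adjustment to be credible, report the comparison within miscarriages.

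The cost is a few sentences of protocol text, consistent recording of routine clinical data, and a few degrees of freedom out of 100 women. SPSS, already named, fits the model. Some precision may be lost if the groups differ in gestational age: under the assumed 1-week gap, adjusted power for 12.6 units is about 85–94% at 60:40 (86–95% at 50:50), against about 89–90% unadjusted. Restricting to miscarriages would reduce the sample by the number of TOPs, which the protocol does not state.

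### Section J names the pooled-variance t-test and ANOVA although the group split is left to chance, and it prints skewed data as median ± IQR; both are minor and cheap to correct

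*Protocol*

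**What the plan says.** Section J (Statistical Analysis) names the tests in one sentence: "Differences between groups will be assessed by Student's t-test, ANOVA and non-parametric test where appropriate". No unequal-variance test is named.

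On description, Section J gives normally distributed data as the mean ± SD or 95% CI, joined by a slash. Skewed data get the median, a ± sign and the "inter-quartile range for skewed distribution".

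Section D (Sample Size) defines two groups by the chromosomal status of the fetus and plans 50 per arm: "Therefore, a total of 100 subjects will be recruited". Sections G and H obtain the genetic result from chorionic villi collected at the procedure, so the group is not known at recruitment. The protocol states no quota or stopping rule per group.

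The only figures on spread are the pilot values in Section D. For the abnormal group it reports: "the CD45+ cell count was 89.7 ± 18.3 in decidual samples from miscarried women with abnormal karyotyping". For the normal group the mean is 102.3 and the SD 20.2. The pilot size is not given.

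**The concern.** **Test.** The pooled standard error is right if the SDs are equal, and close to right if the groups are of equal size. Section D aims at equal groups, but nothing in the protocol secures them. The background says: "Approximately 60% of spontaneous abortions are attributable to numerically abnormal chromosomes in the developing conceptus". That points to roughly 60:40 among miscarriages. Terminations are also eligible, in an unstated proportion, and could move the split the other way. If the smaller group has the larger SD, the pooled test rejects too often; if the larger group has it, too seldom. The flow-cytometry panel in Section I lists about 20 markers for which no SDs are given, so neither the direction nor the size of the error is known for them in advance.

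**Summary of skewed data.** The IQR is one width, Q3 minus Q1. Adding it to and subtracting it from the median gives a symmetric range two IQRs wide, which is not the quartiles. It imposes symmetry on data already judged skewed, and its lower end can fall below zero for a cell count or a cytokine level.

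**Meaning of ±.** For normal data the same sign may stand for spread (SD) or for precision (95% CI), and these differ severalfold.

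**Working it through.** **Inputs.** Section D: means 89.7 (abnormal) and 102.3 (normal), difference 12.6; SDs 18.3 and 20.2, ratio 20.2/18.3 = 1.10; total 100. Background: 60% abnormal among spontaneous abortions. Two-sided alpha of 0.05 is assumed, since the protocol does not state sidedness.

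**The plan's own figure.** The pooled SD is √((18.3² + 20.2²)/2) = 19.27, and 12.6/19.27 = 0.654. At 80% power this needs 37 per arm (38 with the t distribution). Fifty per arm gives about 90% power. That mismatch with "The sample size required for an alpha value of 0.05 and 80% power would be 50 in each arm" is a separate matter. It is noted here because it explains why the powers below are near 90%.

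**How secure is 50:50?** If each of 100 women had a 60% chance of an abnormal result, exactly 50:50 would occur with probability 0.010 (binomial).

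**Type I error with the pilot SDs, by hand.** Compare the variance that Student's test assumes with the true one.

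60 abnormal, 40 normal:
- Pooled variance: (59 × 18.3² + 39 × 20.2²)/98 = 364.0. Assumed variance of the difference: 364.0 × (1/60 + 1/40) = 15.17.
- True variance: 18.3²/60 + 20.2²/40 = 15.78.
- SE ratio: √(15.78/15.17) = 1.020. The effective critical value is 1.984/1.020 = 1.945, a type I error of about 5.5%.

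40 abnormal, 60 normal:
- Assumed variance 15.79, true variance 15.17, SE ratio 0.980. The effective critical value is 2.024, a type I error of about 4.6%.

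**Simulation** (normal data, at least 400,000 trials per setting). The first column uses the pilot SDs; in the other two the normal group's SD is 1.5 or 2 times the abnormal group's, which is an assumption.

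| Abnormal:normal | Pilot SDs (ratio 1.10) | Ratio 1.5 | Ratio 2 |
|---|---|---|---|
| 50:50 | 5.0% | 5.0% | 5.1% |
| 60:40 | 5.4-5.5% | 7.0% | 8.3% |
| 40:60 | 4.6% | 3.5% | 2.8% |
| 70:30 | 6.0% | 9.3% | 12.6% |
| 30:70 | 4.2% | 2.3% | 1.3% |

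Welch's test stays at 4.9-5.1% in every cell.

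**Power at 60:40, difference 12.6.** With equal SDs, Welch's test loses about 0.1 percentage point. With the pilot SDs, Student's test gives 88.9% and Welch's 88.0%. Part of that gap is Student's inflated error rate.

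**Median ± IQR.** Take a log-normal marker with median 1 (an assumption). The quartiles are exp(±0.6745 × log-SD).
- Log-SD 1: quartiles 0.51 and 1.96, IQR 1.45. Median ± IQR runs from -0.45 to 2.45 and covers 82% of the values rather than 50%.
- Log-SD 0.5: quartiles 0.71 and 1.40, IQR 0.69. The range is 0.31 to 1.69, which is positive but still not the quartiles.

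The lower end is negative whenever the IQR exceeds the median.

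**SD or CI after ±.** At n = 50 an SD of 18.3 prints as ±18.3. As a 95% CI it prints as ±2.010 × 18.3/√50 = ±5.2, smaller by a factor of 3.5.

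**The case against.** The strongest reply is that the pilot SDs are close. A ratio of 1.10 from a pilot of unstated size is no evidence of unequal variances: an F-test on those SDs gives p of about 0.77, 0.67 or 0.49 for 10, 20 or 50 per group. At 60:40 the shift is about half a percentage point. The larger figures need SD ratios that the protocol does not report, and Section D assumes that other leucocytes behave much like CD45+. The 60% figure covers spontaneous abortions only, so with terminations included the split could fall near 50:50, where nothing is lost. The test sentence also provides a non-parametric route and a general qualifier, and the choice between Student and Welch is often left to an SAP.

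Most of this stands and sets the severity. A reader might infer from the two pilot SDs that the groups are known to differ in spread; the protocol does not show that. A reader might also count the missing CI for the between-group difference as a fault, but an SAP may supply it.

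Two things remain. Student's t-test is written into the protocol rather than left open, and the only criterion Section J offers is normal versus skewed. Approximately normal data with unequal spread therefore still go to the pooled test. And median ± IQR is a wrongly stated summary under any split, although it affects presentation only and changes no P value.

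**Conclusion.** The point holds as a minor one. The named pooled-variance tests suit a design with secured equal groups, which this is not. For CD45+ the consequence is slight: about 5.5% or 4.6% instead of 5.0% at a 60:40 split either way, and about 6.0% at 70:30. For other markers it would be about 7-8%, or about 3%, at a 60:40 split only if the SD ratio is 1.5-2. That ratio is an assumption, as are normal data and two-sided testing. The stronger reading, that the main P values are materially wrong, is not supported.

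The median ± IQR notation and the double meaning of ± are errors or ambiguities of reporting. The negative lower limit depends on how skewed a marker is; the failure to show the quartiles does not.

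**What to change.** In Section J:

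- For approximately normal markers, name Welch's t-test in place of Student's t-test, and Welch's ANOVA in place of ANOVA if more than two groups are compared. Keep the non-parametric test for skewed markers.
- Report skewed data as median (Q1 to Q3), without ±.
- Use SD for spread within a group, and label any 95% CI separately.

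This takes two or three sentences and no extra data. Naming the test beforehand also removes a choice that could otherwise be made after the split is seen. The cost in power is about 0.1 percentage point if variances are equal and about 1 point at 60:40 with the pilot SDs.

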(1) SNVs calling is carried out by HaplotypeCaller (GATK) and annotated by ANNOVAR (PMID: 20601685) with different public referenced databases. SNV interpretation is performed by referencing the medical literature and online databases according to the guidelines of the ACMG.

(2) For CNV, SV, and AOH analysis, the same pipeline used in ChromoSeq method is applied.

I. Immunological studies on maternal decidua

I. Immunohistochemistry staining

Serial sections will be stained with anti-CD56 antibodies for uNK cells or anti-CD163 antibodies for macrophages. Also, other leucocytes will be determined by immunohistochemistry as well. All primary antibodies will be incubated overnight at 4 °C. The reaction will be developed with 3,3-diaminobenzidine (DAB) containing 0.01% H₂O₂ to give a brown reaction product. Sections will be lightly counterstained with haematoxylin, dehydrated, cleared and mounted with DPX synthetic resin.

II. Multiplex immunofluorescence panel of different immune cell markers

After immunohistochemistry analysis was used for all of the target decidua markers (including different leucocytes), each target was assessed by a uniplex immunofluorescence assay by the Opal 7-color kit to optimize the antibodies and to build up spectral libraries for multiplex immunofluorescence. Slides will be scanned and images will be acquired using the Vectra 3.0 spectral imaging system. The data from the multispectral camera will be accessed and all the leucocytes population from each panel will be characterized and quantified by the imaging InForm software.

III. Serum cytokine measurements

Serum will be separated by centrifugation at 3000 rpm at 4 °C for 10 min and stored at – 80 °C freezers for later measurements. Later, the maternal serum samples will be thawed and centrifuged for measurements of all cytokines and chemokines at the

same time. The Luminex's xMAP® technology, a multiplexed microsphere-based cytometric assay, will be used to examine.

IV. Multicolor flow cytometry

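### Section J applies an unqualified P<0.05 to every group difference, but no outcome is named to decide hypothesis 1; the CD45+ count that sizes the study is never declared the main comparison

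*Protocol*

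**What the plan says.** Section J (Statistical Analysis) assesses group differences by t-test, ANOVA or a non-parametric test as appropriate, and adds: "P value of <0.05 will be considered statistically significant". It names no outcome, gives no order of tests and marks nothing as exploratory.

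Section B states hypothesis 1 globally: "Decidua tissue is different between euploidy pregnancy and aneuploidy pregnancy". The background puts the purpose as finding out "whether decidual leukocyte subpopulations and their associated activation markers were different", which is again plural.

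The decidual readouts are described under Immunological studies on maternal decidua:

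- **Immunohistochemistry:** CD56 and CD163, then "Also, other leucocytes will be determined by immunohistochemistry as well".
- **Multiplex immunofluorescence:** "all the leucocytes population from each panel will be characterized and quantified".
- **Flow cytometry:** 21 named antibodies (counting CD66b and Fox-3 separately), after which the list is left open. CD45 is not among those named.

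Section D (Sample Size) states "There are two groups in this study", chromosomally normal and chromosomally abnormal. It takes pilot CD45+ counts as the basis for 50 per arm. CD45+ enters as a stand-in: "we are making an assumption that the degree to which other leucocytes are affected, is similar to that of CD45+ cell count". It is not called the primary or main outcome there or in Section J.

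**The concern.** A hypothesis that decidua differs, with no stated outcome to decide it, can be supported by whichever population happens to cross 0.05. With a single comparison, that happens by chance 5% of the time when karyotype is unrelated to decidual immunity. With several comparisons under the same unqualified threshold, it happens more often. The protocol does not say which result would count as the answer and which would only suggest further work. A reader of the eventual report could not tell a planned answer from a chance one.

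The concern is about what the protocol fixes: the threshold in Section J, and a hypothesis without a deciding outcome in Section B. It is not a complaint that a detailed multiplicity procedure is absent; that could properly sit in an analysis plan.

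**Working it through.** **1. Inputs from Section D.** Pilot CD45+ count 89.7 (SD 18.3) with abnormal karyotype and 102.3 (SD 20.2) with normal karyotype; alpha 0.05; power 80%; 50 per arm. Sidedness is not stated; two-sided is assumed.

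**2. The plan's own figure.**

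- Difference: 102.3 − 89.7 = 12.6.
- Common SD: √((18.3² + 20.2²)/2) = 19.27.
- Standardised difference: 12.6/19.27 = 0.654.
- n per arm = 2(z₀.₉₇₅ + z_power)² × 19.27²/12.6². For 80% power, 2(1.960 + 0.842)² × 371.5/158.8 = 36.7, so 37. For 90% power, 2(1.960 + 1.282)² × 371.5/158.8 = 49.2, so 50.
- By the exact t-test, 38 per arm is the smallest size that reaches 80%.

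The stated 50 therefore does not reproduce at 80% power. It matches 90% power, or 38 evaluable after a loss of 1 − 38/50 = 24%. The protocol states no such loss allowance. This mismatch is a separate matter and is on the safe side for a single CD45+ comparison.

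**3. Power if CD45+ is the one main comparison.** Two-sided 0.05, noncentral t with noncentrality 0.654 × √(n/2):

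- 50 per arm: noncentrality 3.27, power 89.9%.
- 38 per arm: noncentrality 2.85, power 80.3%.

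**4. Chance of at least one P<0.05 when no marker differs.** For m independent tests this is 1 − 0.95^m. For correlated tests I took normal test statistics with a common pairwise correlation and integrated numerically. Both m and the correlation are assumptions, because the protocol gives neither.

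| Tests | Correlation 0 | 0.5 | 0.8 |
|---|---|---|---|
| 2 | 9.8% | 9.1% | 7.8% |
| 3 | 14.3% | 12.5% | 9.8% |
| 5 | 22.6% | 18.3% | 12.7% |

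Every entry is above 5%. Larger numbers of tests give larger values: ten tests give 17% to 40% over the same range of correlations. The conclusion does not need them, because two tests at high correlation already exceed 5%.

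**5. What is not computed.** The 21 named antibodies are not 21 tests. Flow cytometry reads them by co-localisation, so the number of populations compared could be smaller or larger. No figure is claimed for blood, serum cytokines or transcripts.

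**The case against.** **An analysis plan may cover this.** Only the protocol is at hand, and listing the tests or choosing an adjustment is ordinary analysis-plan content. That stands for the detail. It does not remove the point, because the protocol itself states the threshold and states hypothesis 1 without an outcome that decides it. The threshold sentence does not say that P values will be unadjusted or that one hit settles the hypothesis; but it does not exclude either.

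**Section D already supplies a main comparison.** This stands in part. Section D defines the contrast, and CD45+ count is the only readout with pilot data, an effect and a power target. It would be wrong to say that the protocol offers no candidate. The defect is smaller: the sizing variable is not declared primary, Section J does not mention it, and Section D uses it as a proxy for other leucocytes.

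**The study is investigative.** Both objectives are to investigate, and Section D notes that there are no literature data on the group difference. Unadjusted P values are defensible in such work if they are labelled. Here they are not, and they sit beside formal hypotheses, a powered sample size and a significance threshold. A labelling sentence would cure that part. Formal false-discovery control is a choice on which statisticians differ, so it is not required here.

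**Stronger readings that the protocol does not support.** A reader might count 21 antibodies and infer a false-positive chance of 66% (1 − 0.95²¹). That needs 21 independent tests, and the protocol specifies neither the number nor the independence. A reader might also infer three contrasts per marker from "The baseline characteristics of the three groups of patients will be compared using the Mann-Whitney test". That sentence concerns baseline characteristics only, so it does not show that decidual markers will be compared across three groups.

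**Conclusion.** The point holds in a limited form. Section J's threshold is unqualified, hypothesis 1 has no deciding outcome, the decidual readouts are open-ended, and the variable that sizes the study is not declared the main comparison. If any nominally significant decidual marker may support hypothesis 1, the chance of a false claim is above 5%: about 8% for two tests at correlation 0.8, and 13% to 23% for five tests at correlation 0.8 to 0. These figures assume that no marker differs by karyotype and that test statistics are equally correlated; the numbers of tests are illustrative. The direction is firm for any two or more tests that are not perfectly correlated; the size is not.

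The study can run as designed. What is at risk is whether its answer to hypothesis 1 can be read as a test at the 5% level. This should be corrected before data are compared, because a main comparison chosen afterwards cannot be told apart from a chance finding.

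**What to change.** In Section J, before data are compared:

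1. Name one main decidual comparison for hypothesis 1, chromosomally normal versus abnormal, at two-sided 0.05. The default is the CD45+ count sized in Section D, with its assay and unit stated. The investigators may prespecify another single marker, such as a leucocyte subset or activation marker closer to the purpose in the background. The Section D power would carry over only if that marker has a similar effect.
2. State that all other decidual comparisons are exploratory, and that a nominal P<0.05 among them does not by itself support hypothesis 1.
3. Optionally, list the remaining populations and control their false-discovery rate. This is not a condition of the fix.

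As a separate point, reconcile the three groups in Section J's baseline sentence with the two groups in Section D.

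**Cost.** One paragraph, with 100 subjects unchanged. The main comparison keeps its full 0.05, with about 90% power at 50 per arm and 80% at 38. That power rests on the pilot effect, which came from miscarried women only, while women undergoing termination of pregnancy are also enrolled. The downside is that other markers can no longer be claimed as confirmatory, even if one of them turns out to be the more interesting result.
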